Experimental Studies of Cigarette Graphic Warning Labels: Analysis Plan

1. Respondent Universe and Sampling Methods

The respondent universe for this study is (1) adolescent current cigarette smokers aged 13-17 years old; (2) adolescents who are susceptible to initiation of cigarette smoking aged 13-17 years old; (3) young adult current cigarette smokers aged 18 to 24 years old; (4) young adult nonsmokers aged 18 to 24 years old; (5) older adult current cigarette smokers aged 25 years old and older; and (6) older adult nonsmokers aged 25 years old and older.

Study participants will be recruited from a national online panel of adults managed by Lightspeed. The Lightspeed panel is a non-probability convenience sample recruited via social media, online recruitment (e.g. via banner placements), and affiliate corporate networks. For the current study, Lightspeed will recruit adult panelists and parents of potential youth respondents using information from panelist's user profiles related to study eligibility (i.e. age, smoking status, and whether or not the panelist has a child in the eligible age range).

Lightspeed panel members will receive an email inviting them to participate in the study. Adolescent children of adult panel participants will be invited to complete the survey through an email invitation to their parents asking for their consent to solicit their child's opinions. Panel members and children of panelists who choose to participate will complete the questionnaire. During the study recruitment, we will monitor the sample and can adjust recruitment targeting as needed to ensure the sociodemographic distribution is diverse in terms of age, gender, education, and ethnicity/race. We estimate a total of 9,760 respondents will complete the baseline data collection. We will administer two follow-up surveys of baseline survey participants, with estimated retention rates of between 50% - 100% for each follow-up session (Table 1).

[figure not shown]
Table 1. Estimated Sample Sizes, by Sample Group and Study Session

Age Group	Smoking Status	Session		
		1	2	3
Adolescent	Current Smoker	230	115 - 230	58 - 230
Adolescent	Susceptible to Smoking	2,070	1,035 - 2,070	518 - 2,070
Young Adult	Current Smoker	1,330	665 - 1,330	333 - 1,330
Young Adult	Nonsmoker	1,330	665 - 1,330	333 - 1,330
Older Adult	Current Smoker	2,400	1,200 - 2,400	600 - 2,400
Older Adult	Nonsmoker	2,400	1,200 - 2,400	600 - 2,400
Total		9,760	4,880 - 9,760	2,440 - 9,760

2. Study Protocol

The study comprises three Sessions, outlined in Figure 1.

Figure 1. Study Protocol

In Session 1, participants will first complete a screening questionnaire through an email invitation. After screening for inclusion (see Study Screener), participants who qualify for the study will complete three consecutive components: (1) a baseline assessment of beliefs about the negative health consequences of cigarette smoking; (2) assignment to study condition and exposure to cigarette warning stimuli according to condition assignment; and (3) assessment of new information, self-reported learning, and other reactions to the stimuli (see Session 1 Survey Instrument). These three components are described below.

- *Component (1)*: First, participants will be asked questions about beliefs related to the health consequences of cigarette smoking.
- *Component (2)*: Following the baseline assessment of beliefs, participants will be randomized to one of 16 treatment conditions or a control condition with variation in exposure to cigarette warnings (Table 2 illustrates the targeted Session 1 sample size and allocation across experimental groups, within each age group and overall). Participants in each experimental condition will be exposed to one graphic health warning (GHW), with each condition corresponding to a unique warning from a set of 16. Participants in the control condition will be exposed to a random selection of one of four Surgeon General's (SG) warnings. Each stimuli exposure will include viewing of the warning in two formats: on a mock cigarette package depicted in a 3-dimensional, rotational model; and on a mock cigarette advertisement. In all analyses, stimuli exposure will be considered the joint exposure to both stimuli formats; stimuli format is not considered a study factor
- *Component (3)*: After viewing the warning stimuli in both package and advertisement formats, participants will complete a brief set of measures to assess (a) if the information presented in the warning was new; (b) self-reported learning from the warning; (c) if the warning was easy to understand; (d) if the warning was perceived to be a fact or an

opinion; (e) if the warning was informative; (f) if the warning grabbed their attention; and (g) if the warning made them think about the health risks of smoking.

One to two days following completion of the baseline assessment (Session 1), participants will receive an email invitation to complete a follow-up (Session 2). In this follow-up session, participants will first be re-exposed to the warning stimuli they were shown in Session 1. This exposure will follow the same protocol described in Component 2, above. Following stimuli exposure, participants will complete a set of immediate post-test measures assessing beliefs related to the negative health consequences of cigarette smoking (see Session 2 Survey Instrument). These measures will facilitate an assessment of change in beliefs related to smoking-related health consequences following exposure to the cigarette warning stimuli.

Approximately 14 days later, at the delayed post-test (Session 3), participants will receive an email invitation to complete a questionnaire assessing measures of beliefs about the negative health consequences of cigarette smoking, as well as recall of the warning (see Session 3 Survey Instrument).

Table 2. Condition Assignment and Session 1 Sample Size, by Study Population

Condition	Warning Type	Exposure	Expected Sample Size at Session 1			
			Adolescents	Young Adults	Older Adults	Total
		Random selection of 1 of the following SG warnings:				
0 (Control)	SG	1) SURGEON GENERAL’S WARNING: Smoking Causes Lung Cancer, Heart Disease, Emphysema, and May Complicate Pregnancy. 2) SURGEON GENERAL’S WARNING: Quitting Smoking Now Greatly Reduces Serious Risks to Your Health. 3) SURGEON GENERAL’S WARNING: Smoking by Pregnant Women May Result in Fetal Injury, Premature Birth, and Low Birth Weight. 4) SURGEON GENERAL’S WARNING: Cigarette Smoke Contains Carbon Monoxide.	492	564	1,024	2,080
1	GHW	WARNING: Cigarettes are addictive.	113	131	236	480
2	GHW	WARNING: Tobacco smoke can harm your children.	113	131	236	480
3	GHW	WARNING: Smoking can kill you.	113	131	236	480
4	GHW	WARNING: Tobacco smoke causes fatal lung disease in nonsmokers.	113	131	236	480
5	GHW	WARNING: Quitting smoking now greatly reduces serious risks to your health.	113	131	236	480
6	GHW	WARNING: Smoking causes head and neck cancer.	113	131	236	480

7	GHW	WARNING: Smoking causes bladder cancer, which can lead to bloody urine.	113	131	236	480
8	GHW	WARNING: Smoking during pregnancy stunts fetal growth.	113	131	236	480
9	GHW	WARNING: Smoking can cause heart disease and strokes by clogging arteries.	113	131	236	480
10	GHW	WARNING: Smoking causes COPD, a lung disease that can be fatal. [IMAGE 1: BRAIN]	113	131	236	480
11	GHW	WARNING: Smoking causes COPD, a lung disease that can be fatal. [IMAGE 2: MAN]	113	131	236	480
12	GHW	WARNING: Smoking reduces blood flow, which can cause erectile dysfunction.	113	131	236	480
13	GHW	WARNING: Smoking reduces blood flow to the limbs, which can require amputation.	113	131	236	480
14	GHW	WARNING: Smoking causes type 2 diabetes, which raises blood sugar.	113	131	236	480
15	GHW	WARNING: Smoking causes age-related macular degeneration, which can lead to blindness.	113	131	236	480
16	GHW	WARNING: Smoking causes cataracts, which can lead to blindness.	113	131	236	480
TOTAL			2,300	2,660	4,800	9,760

NOTE: SG = Surgeon General's Warning; GHW = Graphic Health Warning

3. Power Analysis

We conducted power calculations to confirm that the overall sample size (shown in Table 2) is sufficiently powered and to determine the optimal sample size and allocation of sample across study conditions. To control for Type 1 error taking into account multiple testing, power calculations were based on the false discovery rate (FDR) (Benjamini & Hochberg, 1995).

Assuming the tests are independent, the FDR is the expected proportion of significant results that are falsely declared as statistically significant. Controlling the FDR is controlling the expected proportion of falsely declared differences (i.e., false discoveries). Controlling the FDR is a more powerful method for dealing with multiple comparisons than other methods that control the family-wise error rate (Benjamini & Hochberg, 1995).

For the overall study sample size, we calculated power to detect a difference in the change in a tobacco-related belief from Session 1 to Session 2 between treatment and control groups (i.e., difference in difference) (Table 3 provides power estimates for Session 2 across various scenarios). RTI calculated power to detect a 0.3 difference on a 7-point scale (two-sided tests, assuming a standard deviation of 1) under different scenarios with variation in FDR, within-person correlation between Session 1 and 2, and sample allocation. RTI conservatively assumed 50% retention from Session 1 to Session 2. Power calculations were computed using 100 simulations for each sample allocation in SAS v9.4.

Across various assumptions of within-person correlation and FDR, we found generally higher levels of power using an optimized sample allocation with between 1,760 and 2,400 participants assigned to the control condition at Session 1 (880-1,200 participants at Session 2, assuming 50% retention). Based on this analysis showing that higher power is achieved with an unbalanced allocation, FDA plans to allocate 2,080 to the control group and 480 to each treatment group at Session 1.

Table 3. Study Power by Sample Allocation at Session 2

Sample Allocation at Session 2		Within-person Correlation	FDR					Unadjusted Power
Control	Treatment		0.05	0.1	0.15	0.2	0.25	
287	287	0	0.60	0.71	0.83	0.89	0.91	0.68
880	250	0	0.80	0.89	0.94	0.95	0.97	0.85
1,200	230	0	0.77	0.87	0.90	0.94	0.95	0.81
1,520	210	0	0.88	0.92	0.94	0.96	0.98	0.88
1,840	190	0	0.72	0.84	0.88	0.92	0.93	0.78
287	287	0.2	0.64	0.77	0.83	0.89	0.90	0.73
880	250	0.2	0.95	0.95	0.97	0.99	0.99	0.96
1,200	230	0.2	0.89	0.94	0.95	0.98	1.00	0.91

1,520	210	0.2	0.87	0.92	0.94	0.96	0.98	0.89
1,840	190	0.2	0.85	0.88	0.94	0.94	0.99	0.87
287	287	0.4	0.85	0.91	0.96	0.98	0.99	0.89
880	250	0.4	0.97	0.98	0.99	0.99	1.00	0.98
1,200	230	0.4	0.97	1.00	1.00	1.00	1.00	0.97
1,520	210	0.4	0.95	0.97	0.97	0.97	0.98	0.95
1,840	190	0.4	0.91	0.94	0.97	0.97	0.97	0.91
287	287	0.6	0.97	0.98	0.98	1.00	1.00	0.98
880	250	0.6	1.00	1.00	1.00	1.00	1.00	1.00
1,200	230	0.6	1.00	1.00	1.00	1.00	1.00	1.00
1,520	210	0.6	1.00	1.00	1.00	1.00	1.00	1.00
1,840	190	0.6	1.00	1.00	1.00	1.00	1.00	1.00
287	287	0.8	1.00	1.00	1.00	1.00	1.00	1.00
880	250	0.8	1.00	1.00	1.00	1.00	1.00	1.00
1,200	230	0.8	1.00	1.00	1.00	1.00	1.00	1.00
1,520	210	0.8	1.00	1.00	1.00	1.00	1.00	1.00
1,840	190	0.8	1.00	1.00	1.00	1.00	1.00	1.00

Note: FDR = False Discovery Rate

4. Analysis

In the sections that follow, we describe our approach for three phases of analysis: In Phase 1, we will examine how reactions to warnings vary between GHW and SG warnings. In Phase 2, we will conduct a longitudinal analysis to examine the extent to which changes in beliefs vary between those exposed to GHW vs. those exposed to SG warnings. Finally, in Phase 3 we will assess variation in recall of warnings between those exposed to GHW vs. SG warnings. Note that the level of detail provided for each analysis Phase is commensurate with the level of complexity of the according analyses. The Phase 2 analyses involve longitudinal assessments of belief change and include methodological considerations around variable measurement and scaling that warrant more detailed explanation than Phase 1 and Phase 3 analyses.

4.1. Phase 1: Reactions to Warnings (Post-Exposure)

For the Phase 1 analysis, we will conduct comparisons of means and proportions for key reaction measures related to the warnings. Note that participants in the control condition will be exposed to a random selection of one of four Surgeon General’s (SG) warnings; thus, each analysis will compare reaction measure means or proportions for a particular treatment condition to the means or proportions of the control group as averaged across the four SG warnings (i.e., we will compare treatment scores to a single control group score, rather than conducting separate analyses for each SG warning within the control condition). Table 4 provides a summary of the dependent variables, variable treatment, hypothesis, and analysis approach for each variable. Each analysis in this Phase will be repeated for each treatment-control comparison, for a total of

16 analyses per dependent variable.

Table 4. Phase 1 Analyses

Item #	Dependent Variable	Construct	Variable Treatment	Hypothesis	Analysis
B1	Before today, had you heard about the specific smoking-related health effect described in the warning? [Yes / No / I'm not sure]	New information	Dichotomous [Yes (0) vs. No / I'm not sure (1)]	H ₀ : proportion (%) responding that the warning provides new information (had not heard of the information contained in the warning prior to the experimental exposure) for those in the treatment condition = proportion (%) responding that warning provides new information for those in the control condition H _a : proportion (%) responding that warning provides new information for those in the treatment condition ≠ proportion (%) responding that warning provides new information for those in the control condition	Logistic regression
B12	To what extent did you learn something new from this warning that you did not know before? [7-pt scale from 1 (Not at all) to 7 (Very Much)]	Knowledge gain	Continuous	H ₀ : the mean response to B12 for those in the treatment group = the mean response to B12 for those in the control group. H _a : the mean response to B12 for those in the treatment group ≠ the mean response to B12 for those in the control group.	Linear regression
B10	How much does this warning make you	Thinking about Risks	Dichotomous [Somewhat / A	H ₀ : proportion (%) responding that the warning made them think about the health risks of	Logistic regression

Item #	Dependent Variable	Construct	Variable Treatment	Hypothesis	Analysis
	think about the health risks of smoking? [Not at all / A little / Somewhat / A lot]		lot (1) vs. Not at all / A little (0)]	smoking somewhat or a lot for those in the treatment condition = proportion (%) responding that warning made them think about the health risks of smoking somewhat or a lot for those in the control condition H _a : proportion (%) responding that the warning made them think about the health risks of smoking somewhat or a lot for those in the treatment condition ≠ proportion (%) responding that warning made them think about the health risks of smoking somewhat or a lot for those in the control condition	
B8_1	This statement is...[7-pt. scale from 1 (Not at all informative) to 7 (Very informative)] (B8_1)	Perceived informativeness	Continuous	H ₀ : the mean response to B8_1 for those in the treatment group = the mean response to B8_1 for those in the control group. H _a : the mean response to B8_1 for those in the treatment group ≠ the mean response to B8_1 for those in the control group.	Linear regression
B8_2	This statement is...[7-pt. scale from 1 (Hard to understand) to 7	Perceived understandability	Continuous	H ₀ : the mean response to B8_2 for those in the treatment group = the mean response to B8_2 for those in the control group.	Linear regression

Item #	Dependent Variable	Construct	Variable Treatment	Hypothesis	Analysis
	(Easy to understand)] (B8_2)			H _a : the mean response to B8_2 for those in the treatment group \neq the mean response to B8_2 for those in the control group.	
B9	Would you say that this warning statement is an opinion or a fact? [Opinion / Fact]	Perceived factualness	Dichotomous [Fact (1) / Opinion (0)]	H ₀ : proportion (%) responding that the warning is a fact for those in the treatment condition = proportion (%) responding that warning is a fact for those in the control condition H _a : proportion (%) responding that the warning is a fact for those in the treatment condition \neq proportion (%) responding that warning is a fact for those in the control condition	Logistic regression

To test the hypotheses, for each outcome, we will estimate a regression model of the following general form:

$$\text{Outcome} = f(\text{Condition, Age, Smoking Status})$$

where Outcome is a measure of reaction to the warning, Condition is a dichotomous indicator for a treatment versus control condition, Age is a categorical variable for age group (i.e. youth aged 13-17; young adults aged 18-24; and adults aged 25+), and Smoking Status is an indicator for current smoking versus not current smoking (in the adult and young adult samples non-current smokers are never smokers and in the youth sample non-current smokers are those youth susceptible to smoking). These models will include covariates for age and smoking status group to account for potential associations between age, smoking status and outcomes of interest.

The coefficient from the Condition variable indicates whether the outcome was significantly higher among those exposed to a GHW as compared to those exposed to a SG warning. This general model will be repeated for each of 16 treatment versus control group comparisons. All regressions, both logistic and linear will be estimated in Stata version 14.1 and will be estimated using Stata's robust standard errors.

As a supplement to the analyses above, we will conduct parallel analyses stratified by age group (i.e. youth aged 13-17; young adults aged 18-24; and adults aged 25+) and smoking status (current smoker versus non-smoker) to examine potential effects within each age and smoking status group. Of note is that this study is not sufficiently powered to detect within-age-group or smoking status differences, and so results from the stratified analyses should be interpreted with caution (i.e. a non-significant finding within an age or smoking status group may reflect lack of statistical power).

A total of 96 statistical tests will be conducted in Phase 1 (not including supplemental age-stratified analyses). To account for the possibility of falsely detecting a significant result (i.e. Type 1 error) arising from multiple statistical tests, we will control for the False Discovery Rate (FDR) using the Benjamini-Hochberg procedure (assuming a two-tailed test and FDR of 0.05)¹. The Benjamini-Hochberg procedure involves ranking all the p-values from a family of tests from smallest to largest. The smallest p-value has a rank of $i=1$, the next smallest has $i=2$, etc. The next step is comparing each individual p-value to its Benjamini-Hochberg critical value, $(i/m)Q$, where i is the rank, m is the total number of tests, and Q is the FDR you choose. The largest p-value that has $P < (i/m)Q$ is statistically significant, and all of the p-values smaller than it are also statistically significant, even the ones that are not less than their Benjamini-Hochberg critical value. In other words, once a p-value in the list satisfies $P \geq (i/m)Q$, then no other p-values of that value or larger are considered statistically significant (and all less than that value are statistically significant).

There is little guidance on the best FDR to use in a study. Note that for an FDR of 0.05, the smallest p-value needs to be less than what would be the conservative Bonferonni correction (0.05/m), i.e., when $i=1$, then the Benjamini-Hochberg critical value is $(1/m)*0.05$. At an FDR of 0.05, the Benjamini-Hochberg critical value becomes slightly less conservative than a Bonferonni cut-off if p-values are less than this cut-off. However, if no p-values are less than 0.05/m, then no results are statistically significant. Thus, an FDR of 0.05 is conservative, like a Bonferonni correction. Accordingly, we will report results indicating statistical significance using an FDR of 0.05 (most conservative) and using no adjustment for multiple comparisons (least conservative).

We do not anticipate substantial item non-response, nor do we expect that patterns of item non-response would vary significantly among study conditions. Thus, we will plan to use pairwise deletion to include all available data for each particular analysis. We will examine the data for issues of item non-response and differential item non-response and adjust our approach for handling missing data accordingly.

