4.2. Phase 2 Analysis: Condition-level Comparisons of Change in Beliefs

Model 1: Change in Beliefs from Session 1 to Session 2

For the Phase 2 analysis, we will conduct treatment vs. control comparisons of change in beliefs about the negative health consequences of smoking contained in the warnings. Note that participants in the control condition will be exposed to a random selection of one of four Surgeon General’s (SG) warnings; thus, each analysis will compare the change in belief scores between a particular treatment condition and the control group as averaged across the four SG warnings (i.e., we will compare treatment scores to a single control group score, rather than conducting separate analyses for each SG warning within the control condition).

For each experimental condition, the survey includes an item or series of items in which respondents are asked to rate their level of agreement with a statement about a negative health consequence corresponding to the warning for that condition. The number of items associated with a particular warning ranges from 1 to 4. These items are assessed once during Session 1 before stimuli exposure, and then again following second stimuli exposure in Session 2. Table 5 provides a summary of the comparisons, dependent variables, and analysis approach for each of the Phase 2 analyses.

Table 5. Phase 2 Analyses

Analysis #	Comparison	Dependent Variable(s) [All 5-level “Strongly disagree” to “Strongly agree” response options]	Analysis
-------------------	-------------------	---	-----------------

1	Condition 1 vs. Control (0)	A1_1. Cigarettes are addictive	Ordinal logistic regression
2	Condition 2 vs. Control (0)	A2_1. Tobacco smoke can harm your children	Ordinal logistic regression
3	Condition 3 vs. Control (0)	A3_1. Smoking can kill you	Ordinal logistic regression
4	Condition 4 vs. Control (0)	A4_1. Smoking causes fatal lung disease in nonsmokers	Ordinal logistic regression
5	Condition 5 vs. Control (0)	A5_1. Quitting smoking now greatly reduces serious risks to your health	Ordinal logistic regression
6	Condition 6 vs. Control (0)	A6_1. Smoking causes head cancer A6_2. Smoking causes neck cancer	Linear regression (if scaled); ordinal logistic regression (if items treated separately)
7	Condition 7 vs. Control (0)	A7_1. Smoking causes bladder cancer, which can lead to bloody urine A7_2. Smoking causes bladder cancer	Linear regression (if scaled); ordinal logistic regression (if items treated separately)

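### Phase 1 leaves unused a pre-randomisation belief measure that could modestly sharpen some reaction contrasts; the present model is valid, so this is an optional efficiency gain

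*SAP*

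**What the plan says.** Section 4.1 fits each of six reaction outcomes, for each of 16 treatment-control pairs, as a function of condition, age group and smoking status. The stated reason for the covariates is: "These models will include covariates for age and smoking status group to account for potential associations between age, smoking status and outcomes of interest". The total is given as: "A total of 96 statistical tests will be conducted in Phase 1".

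Section 2 (Study Protocol) puts "a baseline assessment of beliefs about the negative health consequences of cigarette smoking" first in Session 1. Assignment comes next: "Following the baseline assessment of beliefs, participants will be randomized to one of 16 treatment conditions or a control condition". The reaction measures follow exposure in the same session. Section 4.2 says of the belief items matched to each warning: "These items are assessed once during Session 1 before stimuli exposure, and then again following second stimuli exposure in Session 2". Table 5 compares every condition with the control group on that condition's own items, so controls answer all of them.

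What controls rate in Phase 1 is a different warning: "Participants in the control condition will be exposed to a random selection of one of four Surgeon General's (SG) warnings". The reaction items refer to the warning that was seen. B1, for example, asks: "Before today, had you heard about the specific smoking-related health effect described in the warning".

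**The concern.** How far someone already agrees that smoking causes a given effect should help to predict whether that effect was new to them (B1), how much they felt they learned (B12), whether they call the warning a fact (B9), how informative they find it (B8_1) and perhaps whether it makes them think about risk (B10). The measure precedes randomisation, so adjusting for it is valid, and no attrition separates it from the outcome. The SAP uses it only as the Phase 2 baseline. The reason it gives for including age and smoking status, association with the outcome, applies to the matched belief as well. What is at stake is precision in some Phase 1 contrasts. Bias is not at issue.

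**Working it through.** **The plan's own figures.** Six outcomes × 16 comparisons = 96 tests: 48 linear (B12, B8_1, B8_2) and 48 logistic (B1, B10, B9). Allocation (Table 2): 2,080 + 16 × 480 = 9,760. Both agree with the SAP. It states no power or precision figure for Phase 1.

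**Inputs.** n_T = 480 and n_C = 2,080, from Table 2. The belief-reaction correlations r_T (graphic-warning arm) and r_C (control arm) are *assumed*, because the SAP does not give them. The correlations in Table 3 are between Session 1 and Session 2 beliefs. Here r means what remains after age group and smoking status. The outcome SD is set to 1 in both arms, so the results are only approximate for binary outcomes.

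**Present model.** Variance V0 = 1/480 + 1/2080 = 0.0020833 + 0.0004808 = 0.0025641, so SE = 0.0506 SD. The 480-person arm contributes 2080/2560 = 81% of this, and it is the arm that rates the matched effect.

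**Belief plus condition × belief, centred at the pooled mean.**

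V = (1 − r_T²)/480 + (1 − r_C²)/2080 + (r_T − r_C)²/2560

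The last term is the cost of estimating the covariate mean. At r_T = 0.3 and r_C = 0.1: 0.0018958 + 0.0004760 + 0.0000156 = 0.0023874, and 0.0023874/0.0025641 = 0.931.

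| r_T | r_C | Variance falls | SE falls |
|---|---|---|---|
| 0.1 | 0.1 | 1.0% | 0.5% |
| 0.2 | 0.1 | 3.3% | 1.7% |
| 0.3 | 0.1 | 6.9% | 3.5% |
| 0.4 | 0.1 | 11.8% | 6.1% |
| 0.5 | 0.1 | 18.1% | 9.5% |
| 0.3 / 0.4 / 0.5 | 0 | 5.9 / 10.6 / 16.5% | |
| 0.3 / 0.4 / 0.5 | −0.1 | 5.1 / 9.4 / 15.0% | |
| −0.3 | +0.3 | 3.5% | |

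**Why the interaction is needed.** With one common slope b = (480 r_T + 2080 r_C)/2560, the variance is (1 − 2b r_T + b²)/480 + (1 − 2b r_C + b²)/2080. With r_C = 0 and r_T = 0.3, 0.4 or 0.5 the gain is only 2.4%, 4.3% or 6.7%. With r_T = −0.3 and r_C = +0.3, b = 0.1875 and the variance *rises* by 10.5%. The control arm rated another warning, so unequal slopes should be expected.

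**Binary outcomes.** In simulated trials at 480 vs 2,080 with a log-odds effect of 0.3 and a belief slope of 0.8 in both arms, adding belief to the logistic model raised the SE of the log odds ratio from 0.102 to 0.109. It moved the estimate from 0.27 to 0.31 and power from 0.76 to 0.82. The adjusted coefficient is a conditional odds ratio, whereas Table 4 states these hypotheses as proportions. The adjusted test should therefore be on standardised proportions.

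**Effect on power.** These are linear outcomes at 0.05/96, the strictest Benjamini-Hochberg step. For an assumed 0.3 SD effect, power is already 0.993. For 0.2 SD it goes from 0.684 to 0.734 at r_T = 0.3, r_C = 0.1. For 0.15 SD it goes from 0.31 to 0.38 at r_T = 0.4, or 0.42 at r_T = 0.5, with r_C = 0.1.

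**The case against.** The strongest reply is that this is a preference. The model is pre-specified, unbiased under randomisation and matches the Phase 3 model, and nothing in section 4.1 is contradicted or left open. That stands. Phase 1 also uses the whole Session 1 sample, without the 50% retention assumed for the Phase 2 power calculation, and no power shortfall is shown. That stands too, although the 0.3 difference in section 3 was set for belief change and not for reactions.

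A reader might infer that all 96 tests are less precise than the data allow. The document does not support this. It gives no belief-reaction correlation. There is no evident reason for prior belief to predict ease of understanding (B8_2, 16 of the 96 tests). Where nearly everyone already agrees, the covariate has little variation to use; addiction and smoking being able to kill are likely examples.

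A reader might also take the covariate to concern the same health effect in both arms. That is true only of the 480 treated. The 2,080 controls rate a Surgeon General's warning, mostly on another effect. This limits the gain but does not remove it, because the small arm carries most of the variance and the interaction allows for unequal slopes.

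Two practical objections also hold. The ordinary robust standard error treats the centring mean as fixed. It would understate the variance by about 3% (0.0000625/0.0021010) at correlations 0.5 and 0.1, and by about 6% (0.0001406/0.0021791) at −0.5 and 0.1. And a plain average of the Table 5 items for each warning would bypass the scaling rule in section 4.2 unless it is declared as a covariate only.

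**Conclusion.** The point holds as an optional efficiency gain. The Phase 1 analysis is valid and the plan contains no error here, but it leaves unused a covariate already collected before randomisation. The likely gain is for B1, B12, B9, B8_1 and possibly B10, mainly for little-known effects. The contrast variance would fall by about 7%, 12% or 18% if the correlation in the graphic-warning arm is 0.3, 0.4 or 0.5 and that in the control arm is 0.1, and by about 1% or less if it is 0.1. These sizes rest wholly on assumed correlations, beyond age and smoking status, and on equal outcome SDs. The document cannot show which outcomes and warnings would benefit.

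**What to change.** In section 4.1, for the comparison of condition k with control:

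- Add the Session 1 belief for warning k and its interaction with condition, with the belief centred at the pooled mean. Form it by the scaling rule in section 4.2, or as a pre-specified mean of that warning's Table 5 items used only as a covariate.
- Keep linear regression for B12, B8_1 and B8_2. For B1, B9 and B10, fit logistic regression and test the standardised difference in proportions, in line with the Table 4 hypotheses.
- Use a standard error that allows for estimating the covariate mean, such as an unconditional marginal-effects variance or a bootstrap.
- State a simple rule for missing Session 1 items, so that no one with a reaction response is dropped.
- Keep the present model as a sensitivity analysis.

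The cost is SAP wording and somewhat more analysis work, with no new data. The covariate will differ from one comparison to the next, which makes reporting slightly less tidy. The choice should be fixed before results are seen.
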